## 5.3 Handling of Missing Data

All attempts will be made to limit the amount of missing data. Imputation for specific endpoints are outlined in the description of each endpoint. Unless otherwise specified, no attempt will be made to impute missing data. If a data point is missing, that data point will not contribute to that portion of the analysis. The number of evaluable observations will be reported in analysis so that extent of missing data can be assessed.

## 5.4 Subject Disposition

The number of subjects in each analysis population will be presented along with reason for any exclusions. Subject accountability will be summarized by visit. The number of subjects who are enrolled, eligible for follow-up, and number completing clinical follow-up will be summarized for each protocol-required visit. In addition, the number of subjects who complete the study or exit early will be summarized by reason.

## 5.5 Demographics and Baseline Characteristics

Descriptive statistics will be presented for all clinically relevant baseline demographic, medical history, and clinical characteristic variables.

## 5.6 Analysis of Study Endpoints

There is one primary endpoint and four secondary endpoints. Formal statistical hypothesis tests are planned for the secondary endpoints.

The overall type I error rate will be maintained via a gatekeeping approach whereby statistical tests will proceed in order until a non-significant test is obtained, at which point, formal testing for the purposes of labeling claims will cease.

St	atistical Analysis Plan	Pa	ge 8 of 13
Sponsor	Study		Version
Cochlear Americas	A pivotal, prospective, multi-center, label study evaluating the safety effectiveness of the Cochlear ™ Os System in a pediatric population	and sia ® 2	1.0

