Lau et. al. 2020 reported on the surgical and audiological outcomes using the Osia System in the first 10 United Kingdom patients. Five females and five males participated with a mean age of 52 years (range 30 – 78) who presented with either mixed (n = 5) or conductive hearing losses (n = 3) or single sided deafness (n = 2). All subjects had prior hearing aid experience and were fit with a Baha 5 Power for aided testing prior to implantation with the Osia system. Audiometrically, there was no alteration of the bone conduction thresholds post implantation. Additionally, when the subjects were segmented into the three different audiological indications, the mean gain was + 86.5 dB (range 79–94, SD = 10.6) for single-sided deafness, + 31 dB (range 12–48, SD = 17.3) for mixed and + 22 dB (range 12–31, SD = 9.5) for conductive. The mean functional gain improvement for the study population was +39.4 dB. The authors state that the enhancement in gain appeared to be one of the largest gains amongst bone conduction devices especially in the higher frequencies. Speech recognition as measured by SRT went from 38.1 dB to 22.7 dB at 4 months post-surgery. In addition to objective assessments of outcome, patient-reported outcomes measured by use of the Client Oriented Satisfaction Inventory (COSI) indicated that being able to hear well in real-life situations as well as a decrease in hearing aid disability were significant findings.

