### 6.3.2 Performance/Effectiveness

### 6.3.2.1 Description of Audiometric Testing

Preoperatively, unaided audiometric thresholds will also be obtained in sound field using narrowband noise. Postoperatively at Device Fitting Visit 2, unaided bone conduction thresholds will be obtained as described in section 6.3.1.2 in the implanted ear to assess the impact of implantation and aid in the fitting of the sound processor. The contralateral ear will be masked accordingly.

• Unaided Sound Field Thresholds: 500, 1000, 2000 & 4000Hz

Aided audiometric thresholds will be obtained preoperatively and in the postoperative aided condition using narrowband noise in sound field. The contralateral ear will be plugged for all tests.

Aided Sound Field Thresholds: 500, 1000, 2000 & 4000Hz

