# 8 STATISTICAL CONSIDERATIONS

### 8.1 General Considerations

There is one primary endpoint and four secondary endpoints. Formal statistical hypothesis tests are planned for the secondary endpoints.

The overall type I error rate will be maintained via a gatekeeping approach whereby statistical tests will proceed in order until a non-significant test is obtained, at which point, formal testing for the purposes of labelling claims will cease. A detailed summary of statistical analysis is documented in the Statistical Analysis Plan (SAP).

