#### Secondary

- To compare preoperative performance compared to postoperative performance in parental questionnaires using the Osia 2 System.
- To compare preoperative unaided bone conduction thresholds to postoperative unaided bone conduction thresholds.
- To compare unaided preoperative speech perception performance to aided speech perception performance postoperatively using the Osia 2 System.
- To compare unaided preoperative adaptive speech in noise performance to aided adaptive speech in noise performance using the Osia 2 System.

St	atistical Analysis Plan	Pa	ge 6 of 13
Sponsor	Study		Version
Cochlear Americas	A pivotal, prospective, multi-center, open- label study evaluating the safety and effectiveness of the Cochlear ™ Osia ® 2 System in a pediatric population		1.0

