#### 5.6.3 Secondary Endpoint 2 – PTA

Secondary endpoint 2 is defined as the mean difference in individual subject PTA 500, 1, 2, and 4kHz Baseline to 4 Weeks post-surgery.

### 5.6.3.1 Primary Analysis of Secondary Endpoint 2

The secondary endpoint 2 will be assessed with the following hypothesis:

 $H_0$ :  $\Delta \leq 0$ 

 $H_a$ :  $\Delta > 0$ 

where  $\Delta$  represents difference between baseline PTA and 4 Weeks-post surgery PTA, specifically  $\Delta$  =  $PTA_{4 \ Weeks}$  –  $PTA_{preop}$ . This difference is parameterized so that a positive value is indicative of a clinical improvement.

The hypothesis will be evaluated using a one-sample, one-sided 0.025 alpha level t-test for a mean against the null of zero. The objective will be met if the null hypothesis is successfully rejected.

The endpoint will be presented with descriptive statistics and the corresponding two-sided 95% confidence interval based on the t-distribution.

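### The testing order puts the 4-week PTA second; read as unaided bone conduction, it would probably deny CNC words and BKB-SIN a formal label test

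*SAP*

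**What the plan says.** CIP 8.1 and SAP 5.6 describe one gatekeeping chain for all the formal tests. In SAP 5.6, "statistical tests will proceed in order until a non-significant test is obtained, at which point, formal testing" ends. The stop concerns labelling claims: "formal testing for the purposes of labeling claims will cease". Neither section lists the sequence. The endpoints are numbered SSQ Parent (1), PTA (2), CNC words (3) and BKB-SIN (4) in CIP 8.2.2 and SAP 5.6.2 to 5.6.5, and this numbering is the only order available.

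SAP 5.6.3 gives the second endpoint: "Secondary endpoint 2 is defined as the mean difference in individual subject PTA 500, 1, 2, and 4kHz Baseline to 4 Weeks post-surgery". It does not say which thresholds make up the PTA. The second of the four secondary objectives (CIP 5.2, SAP 2) is "To compare preoperative unaided bone conduction thresholds to postoperative unaided bone conduction thresholds". CIP 6.3.2.1 says the Visit 2 bone-conduction measurement is made "to assess the impact of implantation and aid in the fitting of the sound processor".

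CIP 8.3.2.2 and SAP 5.6.3.1 test this endpoint with a one-sample t-test against zero at one-sided 0.025. The difference is 4 weeks minus preoperative, a positive value is called improvement, and the objective counts as met only if the null is rejected. No non-inferiority margin is given.

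**The concern.** In a fixed sequence, each test decides whether the later ones take place. A test belongs early if it is likely to succeed or if its claim matters most. If endpoint 2 is unaided bone conduction, it is neither. It checks whether implantation affected the cochlear thresholds, and the good outcome is no change. The one earlier result on this measure in the CIP is that "there was no alteration of the bone conduction thresholds post implantation". A trial that preserved hearing perfectly would give a non-significant result in second place, and the chain would stop there.

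At stake is formal inference on speech in quiet and speech in noise. CIP 6.1 names these, with the parental inventory and audibility, as what the secondary endpoints use to assess effectiveness. Under the present order their formal tests depend on a measure that the device is not described as improving.

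**Working it through.** **Which measure.** For unaided bone conduction: the four objectives match the four endpoints one to one and in order; no objective covers aided thresholds; and the Schedule of Events repeats the bone-conduction audiogram after surgery only at Visit 2, the endpoint's time point. The calculation below uses this reading first.

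**Inputs.** n = 50 (SAP 4); one-sided alpha 0.025 and one-sample t-test (SAP 5.6.3.1); expected change zero (CIP 3.2.2.1). The documents give no SD for the change, so effects are in SD units and the non-zero values are assumptions.

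**The plan's own figure.** SAP 4 gives a 95% confidence half-width of 0.284 SD. Check: t(0.975, 49)/√50 = 2.0096/7.0711 = 0.2842. It reproduces. It is also the gate's threshold: endpoint 2 passes only if the observed mean difference exceeds 0.284 observed SDs.

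**Chance that the gate opens.** This is P(T > t(0.975, n−1)), where T is noncentral t with n−1 degrees of freedom and noncentrality d√n. If a true improvement is a fall in threshold, the sign as written makes d negative.

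| True improvement | Noncentrality, n=50 (sign corrected) | Sign corrected | Sign as written |
|---|---|---|---|
| 0 | 0 | 2.5% | 2.5% |
| 0.1 SD | 0.707 | 10.3% | 0.4% |
| 0.2 SD | 1.414 | 28.3% | 0.04% |
| 0.3 SD | 2.121 | 54.8% | below 0.04% |

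At zero change the result equals alpha at every n. With the sign corrected, 0.2 SD and n=40 give 23.4%. At n=50, an 80% chance needs a true improvement of about 0.40 SD.

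**Chance of reaching CNC.** This is P(SSQ passes) × P(PTA passes) if the two are independent. The earlier pediatric study reports a mean SSQ gain of 2.10 (CIP 3.2.2.2) without an SD. With an assumed SD of 3 or less, SSQ passes at least 99.8% of the time; with SD 5, 82.9%. At zero bone-conduction change, the chance of reaching CNC is therefore between 0.829 × 0.025 = 2.1% and 2.5%. Correlation hardly matters: 20,000 simulated trials at each of the correlations 0, 0.3 and 0.6, with assumed effects of 0.8 SD for SSQ and CNC, gave 2.4% to 2.7%.

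**With endpoint 2 last or removed.** CNC is reached whenever SSQ passes: at least 99.8% for an SSQ SD up to 3, 95.3% for SD 4, 82.9% for SD 5. Once reached, a CNC effect of 0.5 SD is detected with 93.4% power. A prespecified sequence still holds the family-wise error at one-sided 0.025.

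**The other reading.** If PTA is aided sound-field against an unaided baseline, the earlier study's 31.7 dB audibility gain is the nearest guide, with an assumed SD of 8 to 40 dB. At SD 40, d = 31.7/40 = 0.79 and a sign-corrected test passes with probability above 99.9%. With the sign as written, d = −0.79 and the probability is effectively zero.

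**The case against.** The strongest answer is that endpoint 2 may not be bone conduction at all. Its four frequencies are exactly the sound-field set in CIP 6.3.2.1, whereas bone conduction is measured at five, including 3 kHz. The endpoint runs from Baseline, where the Schedule of Events places sound-field testing; the bone-conduction audiogram is at Screening. CIP 3.2.2.2 uses PTA 4 for an audibility gain, and CIP 6.1 lists audibility among the effectiveness domains. Aided sound-field thresholds are also taken at Visit 2. This stands: the text does not settle the measure, so a reader who infers that the order is harmful under any reading goes too far.

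Three further limits also stand.

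- A reader might take 10% and 28% as properties of the test now specified. They assume a corrected sign; as written, the figures are 0.4% and 0.04%, and much of the present blockage comes from the sign.
- A reader might infer that the speech results would be lost. Only formal testing for labelling stops. CIP 8.6.2 still reports both with descriptive statistics and 95% confidence intervals, type I error stays controlled, and the primary endpoint is safety with no hypothesis test.
- The evidence for zero change is one series of 10 adults aged 30 to 78, and the sequence itself is inferred from the numbering.

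These limits narrow the point without removing it. The objective and the stated purpose of the Visit 2 test both point to bone conduction, and nothing in the documents predicts that it improves.

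**Conclusion.** The point holds on condition that endpoint 2 is the unaided bone-conduction comparison named in the matching objective and that the order follows the numbering. A superiority test with no expected effect then controls access to both speech tests, and it opens with probability 2.5% at zero change and 28% at a sign-corrected 0.2 SD (n=50). CNC and BKB-SIN would probably go without a formal label test.

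Under the sound-field reading with an unaided baseline and the sign corrected, the gate would almost surely open and there would be no ordering problem. Moving the endpoint to the end would still cost the speech endpoints nothing.

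Two stronger conclusions are not supported. Correcting the sign of endpoint 2 alone does not cure the bone-conduction case, since the pass probability at zero change stays 2.5%. Reordering alone does not rescue BKB-SIN, because its difference has the same sign fault: a lower SNR-50 is the better score. Nor do the documents list the label claims the sponsor wants, so they cannot show that a claim from endpoint 2 would be worthless.

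**What to change.** Before the 6-month database lock (CIP 13.3):

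1. Name the measure in endpoint 2 in the CIP synopsis, CIP 8.2.2.2 and SAP 5.6.3, including test condition, baseline assessment and frequencies.
2. In CIP 8.1 and SAP 5.6, state the order explicitly as SSQ, CNC words, BKB-SIN, with endpoint 2 last or outside the chain.
3. If the measure is bone conduction, revise CIP 8.3.2.2 and SAP 5.6.3.1 so that the objective is assessed by the mean change with its 95% confidence interval, or by non-inferiority with a justified margin. The documents give no margin. Purely as illustration, with 5 dB, no true change and n=50, such a test passes 93.4% of the time at an assumed SD of 10 dB and 99.6% at 7.5 dB.
4. Correct the signs of endpoints 2 and 4 as a separate change.

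The cost is a short SAP revision and a CIP amendment, with the investigator agreement and the ethics committee and regulator notifications that CIP 17 requires. The sponsor gives up an early label claim from endpoint 2. Deleting the test without item 3 would leave that objective with no success criterion.

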#### 5.6.1 Primary Endpoint

The primary endpoint is device and procedure related adverse events Surgery through Visit 4 (6 Months). Events will be summarized by type, frequency, and severity.

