### CIP | VV-TMF-02337 | 5.0 Approval Date (GMT+0): 06 Nov 2023

•	Cochlear employees or employees of Contract Research Organizations or contractors engaged by Cochlear for the purposes of this investigation.
•	Currently participating, or participated within the last 30 days, in another clinical investigation involving an investigational
•	Individuals undergoing simultaneous single-stage aural atresia or microtia repair due to the increased risk of skin complications associated with ear reconstruction.

Primary objective(s)	To demonstrate the safety of the Osia 2 System in a pediatric population aged $5 - 11$ years by quantifying the type, frequency and severity of adverse events.	
Secondary objective(s)	
 
To compare preoperative performance compared to postoperative performance in parental questionnaires using the Osia 2 System.
 
To compare preoperative unaided bone conduction thresholds to postoperative unaided bone conduction thresholds.
 
To compare unaided preoperative speech perception performance in quiet to aided speech perception performance postoperatively using the Osia 2 System.
 
	
	
 
To compare unaided preoperative adaptive speech in noise performance to aided adaptive speech in noise performance using the Osia 2 System.
 
	
Primary endpoint(s)	To quantify the type, frequency and severity of adverse events and serious adverse events Surgery through Visit 4 6 Months post-surgery.	
Secondary endpoint(s)	
 
Mean difference between preoperative Baseline performance on the Speech Spatial & Qualities of Hearing Questionnaire (SSQ) – Parent version to Visit 4 6 Months post-surgery
 
	
	
 
Mean difference in individual subject PTA 500, 1, 2, and 4kHz Baseline to Visit 2 4 weeks post-surgery.
 
	
	
 
Mean difference between Baseline unaided speech perception in quiet and the aided condition using the Osia 2 system at Visit 4 6 Months post- surgery on open-set monosyllabic word recognition (CNC Words) in quiet.
 
	
	
 
Mean difference between baseline unaided speech perception in noise and the aided condition using the Osia 2 system at Visit 4 6 Months post- surgery on an adaptive speech in noise test (BKB SIN).
 
	

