### 8.2 Endpoints

### 8.2.1 Primary Endpoint

The primary endpoint is adverse events and serious adverse events Surgery through Visit 4 (6 Months). Events will be summarized by type, frequency, and severity.

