# **10** Adverse Events and Device Deficiencies

### 10.1 Definitions

### 10.1.1 Adverse Event

An adverse event (AE) is any untoward medical occurrence, unintended disease or injury, or untoward clinical signs (including abnormal laboratory findings) in subjects, users or other persons whether or not related to the medical device or the procedures required for implant or use, and whether anticipated or unanticipated.

NOTE 1: This definition includes events related to the medical device or the comparator device.

NOTE 2: This definition includes events related to the procedures involved.

NOTE 3: For users and other persons, this definition is restricted to events related to the use of medical devices.

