#### **Primary**

 To demonstrate the safety of the Osia 2 System in a pediatric population aged 5 – 11 years by quantifying the type, frequency and severity of adverse events

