#### 5.6.1.1 Primary Analysis of the Primary Endpoint

There is no formal hypothesis test for the primary endpoint.

The endpoint will be presented in tabular format, displaying the number and percentage of subjects with adverse events. Events will also be summarized by type and severity. Results will be based on observed events without imputation.

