## 5.7 Poolability Analyses

All investigational sites will follow the requirements of a common protocol and standardized data collection procedures and forms. The primary and secondary endpoints will be presented separately for each site using descriptive statistics. Poolability of the primary endpoints across investigational sites will be evaluated using a regression model with fixed effects for site. For the primary endpoint, analysis will be based on the proportion of subjects experiencing a procedure or device related adverse event and a logistic regression approach. For the secondary endpoint, a linear regression approach will be used. If the p-value for the site effect is 0.15, additional exploratory analyses will be performed to understand any variations in outcomes by site.

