## 5.9 Subgroup Analyses

Subgroup analysis of the primary and secondary endpoints will be performed for the following subgroups: sex, race (white vs. non-white), age at implantation and etiology of hearing loss. These analyses are intended to demonstrate consistency of results across subgroups.

For the primary safety endpoint, analysis will be based on the proportion of subjects experiencing a procedure or device related adverse event and a logistic regression approach.

Statistical Analysis Plan		Page 13 of 13	
Sponsor	Study		Version
Cochlear Americas	A pivotal, prospective, multi-center, open- label study evaluating the safety and effectiveness of the Cochlear ™ Osia ® 2 System in a pediatric population		1.0

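### The SAP narrows the protocol's primary safety endpoint from all adverse events to device- and procedure-related ones, so the SAP's primary percentage is not the one the protocol defines

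*SAP*

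**What the plan says.** **Protocol.** The synopsis gives the primary endpoint as "To quantify the type, frequency and severity of adverse events and serious adverse events Surgery through Visit 4 6 Months post-surgery". Section 8.2.1 agrees: "The primary endpoint is adverse events and serious adverse events Surgery through Visit 4 (6 Months". Neither mentions relatedness. Section 10.1.1 defines an AE as an untoward occurrence "whether or not related to the medical device or the procedures required for implant or use", so unrelated events belong to the endpoint.

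**SAP.** Section 5.6.1 defines the endpoint over the same window as "The primary endpoint is device and procedure related adverse events Surgery through Visit 4 (6 Months". The restriction recurs. For the primary endpoint in section 5.7 (poolability), "analysis will be based on the proportion of subjects experiencing a procedure or device related adverse event"; section 5.9 (subgroups) says "For the primary safety endpoint, analysis will be based on the proportion of subjects experiencing a procedure or device related adverse event". The SAP's primary objective, in section 2, is to show safety "by quantifying the type, frequency and severity of adverse events", without the restriction. The table described in 5.6.1.1 is one "displaying the number and percentage of subjects with adverse events".

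**Causality.** Protocol 10.2.2 has five grades: not, unlikely, possibly, probably and definitely related. Neither document says which grades make an event related for the SAP's endpoint.

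**The concern.** Safety is the only primary objective, and the primary endpoint has no hypothesis test (protocol 8.3.1, SAP 5.6.1.1). The reported percentage and its breakdown are therefore the primary result. Two documents that define it differently lead to two different primary tables. The SAP's version leaves out any child whose only AEs were judged unrelated, and any SAE so judged.

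The SAP's version also depends on a causality judgement that the protocol's does not need. The study is open-label and the investigator assigns the grade. Protocol 8.8 plans the regulatory submission on the 6-month data, so the definition has to be fixed before those data are locked.

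**Working it through.** **1. The definitions side by side.**

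| Place | Events counted | Window |
|---|---|---|
| Protocol synopsis | AEs and SAEs, no restriction | Surgery to Visit 4 |
| Protocol 8.2.1 | AEs and SAEs, no restriction | Surgery to Visit 4 |
| SAP 5.6.1 | Device- *and* procedure-related AEs | Surgery to Visit 4 |
| SAP 5.6.1.1 | AEs; restriction not repeated | That of the endpoint |
| SAP 5.7, 5.9 | Procedure- *or* device-related AEs | That of the endpoint |

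The windows agree and the event sets do not. Related SAEs stay inside the SAP definition, because an SAE is an AE. Unrelated AEs and unrelated SAEs drop out. The SAP's own shift from *and* to *or* should be settled in the same edit.

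**2. Direction and size.** Let *A* be the number of implanted children with at least one AE and *R* the number with at least one AE counted as related. Every child in *R* is also in *A*, so R/n ≤ A/n whatever the cut-off. With k = A − R, the gap is k/n. Assuming that all 50 planned children are implanted and in the denominator:

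- k = 0: 0/50 = 0 points
- k = 1: 1/50 = 2 points
- k = 5: 5/50 = 10 points
- k = 10: 10/50 = 20 points

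These k values are illustrations; the documents give none. Protocol 3.2.2.2 reports an earlier pediatric study with 15 AEs in 14 subjects, but no split by subject or relatedness. Those counts fit anything from 1/14 = 7.1% to 14/14 = 100% of subjects having an AE, so they do not bound k.

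**3. The plan's own figures.** Protocol 8.4 and SAP 4 claim a probability above 95% of seeing at least one event that occurs at a 5.9% rate in 50 subjects. The check is 1 − (1 − 0.059)^50 = 0.952, which reproduces. The stated 95% confidence half-width of 0.284 also reproduces: t(0.975, 49)/√50 = 2.0096/7.0711 = 0.284. Neither figure depends on which definition is used, so the sample size rationale is untouched.

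**4. Is there a recorded reason for the difference?** SAP section 1 says it was written against protocol version 3.0; the protocol in hand is 5.0. The protocol's change history lists updated AE definitions at version 4 and no change to the primary endpoint at any version. Version 3.0 itself is not available, so this rests on the log alone.

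**5. Can the SAP definition be applied as written?** Not without a further rule, because five grades must become two. Section 10.2.2 sends cases that cannot be assessed to the *possibly related* grade, so whether that grade counts could matter. Section 10.2 collects an opinion on relationship to both device and study procedures. Section 10.2.2 introduces its scale for the Osia 2 system, and its three middle grades speak only of the device. How relationship to procedures is graded is therefore not clear.

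**The case against.** The best defence is that little depends on this. No test, margin or alpha is attached to the endpoint. Protocol 8.7 and SAP 5.8 tabulate all AEs and SAEs and summarise them by relatedness, so the protocol's content would appear in the report. All of that stands, and it limits the stakes. It does not remove the conflict: those sections do not name the surgery-to-Visit-4 window or designate their tables as primary.

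Several stronger readings are tempting, and the documents do not support them:

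- *The SAP contradicts itself.* Section 5.6.1.1 sits under 5.6.1 and presents the endpoint just defined, so it can inherit the restriction. The objective is a general aim that a related-only endpoint could serve.
- *The outcome in the site and subgroup models is undecided.* SAP 5.7 and 5.9 name it. Only the meaning of *related* is open.
- *The relatedness summaries in protocol 8.7 and SAP 5.8 need a cut-off.* A table by the five grades would satisfy them.
- *The version gap cannot explain the difference.* The log records no such change, but version 3.0 cannot be checked. The SAP's version history also mentions a revision after FDA study design considerations, whose content is not shown.
- *The sponsor is free to choose the definition after seeing attributions.* SAP section 6 calls for changes to go through an amended SAP, approved before the analysis when possible, or to be justified in the report. That limits such freedom, though it does not say which definition holds now.

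**Conclusion.** The conflict is real. The protocol's primary endpoint covers all AEs and SAEs from surgery to Visit 4; the SAP's covers only those related to device or procedure. The SAP's percentage can only be equal to or lower than the protocol's. The size is unknown and may be zero: 2 points per affected child if 50 children are analysed.

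The consequence is confined to which result carries the primary label at the 6-month submission. A reader might infer that unrelated events would go unreported, or that error control or power is harmed; neither follows. The missing cut-off for *related* is a secondary gap that matters only where the related-only proportion is used. The conclusion rests on the current texts. Where the SAP wording came from cannot be established from them.

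**What to change.** Before the 6-month database lock (protocol 13.3):

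1. Align SAP 5.6.1 and 5.6.1.1 to the protocol: the count and percentage of implanted children with one or more AEs, and separately with one or more SAEs, from surgery through Visit 4.
2. Keep the device- or procedure-related proportion as a named supporting analysis over the same window.
3. Have SAP 5.7 and 5.9 either use the primary definition or say that they model the supporting one.
4. Wherever the related-only proportion is used, list the recorded causality grades that count as related, settle *and* versus *or*, and confirm how relationship to procedures is graded.
5. If related-only is truly intended as primary, amend protocol 8.2.1 and the synopsis instead; item 4 then applies to the primary endpoint.

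Items 1 to 3 are changes of wording, since all AEs are recorded from implantation. Item 4 needs a check of how the case report form captures relationship to procedures; the documents do not show that this is already settled. Item 5 would need a protocol amendment. The price of the preferred route is that the primary percentage may be higher than under the SAP's definition.
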